### 8.3. Screen Failures

Screen failures are defined as participants who consent to participate in the clinical study but are not subsequently entered in the study.

Individuals who do not meet the criteria for participation in this study (screen failure) may be rescreened once at the discretion of the Investigator.

A minimal set of information will be collected on all screen failures who were never chosen for participation: demography, screen failure details and eligibility criteria.

**PART A:** Evaluate the safety and tolerability of multiple ascending single doses of LAT8881

[figure not shown]
Randomised, placebo controlled ascending dose.

Data safety review, decision on dose for Part 2.

Blood Sampling Visit also required on Day 3 and 6

**PART B:** Evaluate the efficacy of Lat8881 in participants with lumbar radicular pain.

*2 night observation (unless waived by Investigator)*

Randomised, crossover

## 9. STUDY PROCEDURES

### 9.1. Recruitment

Participants will be recruited from the PARC Clinical Research database along with advertising for Part B of the study.

### 9.2. Informed Consent

Potential participants will be provided with the Participant Information and Consent Form (PICF) and given adequate opportunity to read this document, consult with anyone they wish, and to ask questions of the study team, before deciding whether or not to take part. A signed consent form will be obtained from each participant prior to performing any study-specific procedures, including screening activities. Informed Consent must only be received by study

---

team members designated to this duty on the site Delegation Log. In most cases, the Site Principal Investigator or sub Investigators will be responsible for receiving Informed Consent for the study. The original copy of the PICF will be retained in the Investigator Site File and a copy will be provided to the participant. The date of consent, as well as document version and date will be recorded on the Electronic Data Capture (EDC).

### 9.3. Screening

For Part A, the screening visit must occur no more than 60 days prior to dosing.

For Part B, the screening visit must occur no more than 28 days prior to dosing.

For Part B; if the investigator deems appropriate the screening assessments may be split over two visits with Informed Consent Form, Medical History, Sciatic Pain Review and CT or MRI completed prior to additional assessments.

### 9.4. Randomisation

The results of all assessments conducted in the screening visit will be recorded in the EDC and must be reviewed by the Site Principal Investigator to confirm eligibility prior to randomising a patient to the study. Once the Site PI confirms participant eligibility for the trial, the participant will undergo randomisation.

The methodology for assigning study numbers is discussed in section 14.1 below.

### 9.5. Follow Up

Participants will be requested to complete a Follow-Up Visit 1 week after the end of the treatment period (Day 14 for Part A and Day 9 for Part B). The focus of this visit will be completion of safety assessment and monitoring of AE's and Concomitant medications.

## 9.6. ASSESSMENTS

### 9.6.1. Demography

Collection of the participants details including initials, gender, age, race, ethnicity

### 9.6.2. Physical Exam

A complete physical examination will include, at a minimum, assessments of the General Appearance, HEENT, Neck (incl Thyroid), Cardiovascular, Respiratory, Gastrointestinal, Renal, Neurological, Musculoskeletal, and Skin. Height and weight will also be measured and recorded at the Screening Visit.

A Symptom Directed Physical Exam will be performed if necessary at the Day 7 Follow Up and/or ETV.

### 9.6.3. Medical History

A complete medical history will be reviewed at Screening and will include evaluation for past or present cardiovascular, respiratory, gastrointestinal, renal, hepatic, neurological, endocrine, metabolic, lymphatic, hematologic, immunologic, dermatologic, psychiatric, genitourinary and surgical history or any other diseases or disorders (including cancer).

### 9.6.4. Sciatic Pain Assessment and History for Part B

In addition to the physical exam assessment of sciatic pain and history will occur at the screening visit for participant in Part B.

Special attention will be required during the examination of the lower back and neurologic assessment of the lower limbs. This will particularly seek to determine motor function in the affected leg and will assess and record any sensory change that might coincide with the dermatomal representation of the affected nerve root. Assessment will include straight leg raise and qualities of pain in affected leg.

### 9.6.5. Prior and Concomitant Medications

Prior medications are those medications that are initiated and stopped prior to first study drug administration, while concomitant medications are medications taken at least once after first study drug administration. All medications stopping on the same day as first study treatment will be considered as concomitant medications. SARS-CoV-2 vaccination is acceptable, if > 2 week prior to dosing.

### 9.6.6. Vital Signs

Vital signs include blood pressure, heart rate, pulse oximetry, temperature, and respiratory rate (in semi supine or supine position after a 5-minute rest). Vital signs will be collected at the timpoints in Schedule 1 and 2.

### 9.6.7. Electrocardiograms

Electrocardiogram values will be summarized at each protocol scheduled time point. In addition, a frequency tabulation of ECG results (Normal, Abnormal Not Clinically Significant or Abnormal Clinically Significant) will be presented at each protocol scheduled time point.

### 9.6.8. Average Daily Pain Scores (NRS) for Part B

Study staff will contact the participant at the same time each day for 3 consecutive days during the week prior to Day 1 to obtain the participants average leg pain scores for the preceding 24 hours. Pain scores need to be at least  $\geq 3/10$  each day however the 3 day mean must meet the inclusion criteria of between  $\geq 4/10$  and  $\leq 9/10$ .

### 9.6.9. Clinical Safety Blood and Urine

Urinalysis, Urine Drug Screen and Pregnancy testing will occur at Screening, prior to each dosing occasion and Follow up visit or ETV, if applicable.

For Part A only, Local laboratory Clinical Safety Blood results from samples taken on Day 3 and 6 are required to be available and reviewed by PI/ designee prior to dosing occasions 2 and 3.

The following bloods will be performed via a locally contracted pathology laboratory (local laboratory):

Laboratory Tests	Parameters				
Hematology	Haemoglobin Red blood cell count (RBC) Red cell distribution width (RCD) Haematocrit/Packed cell volume (PCV)	RBC Indices: Mean cell volume (MCV) Mean corpuscular haemoglobin (MCH) Mean platelet volume (MPV) Platelets	White blood cell (WBC) count with Differential: Neutrophils Lymphocytes Monocytes Eosinophils Basophils		
Clinical Chemistry	Sodium Potassium Chloride Bicarbonate Anion Gap Urea Creatinine	Albumin Alkaline phosphatase (ALP) Gamma-glutamyl transferase (GGT) Alanine Aminotransferase (ALT)	Creatinine Kinase		
	eGFR Uric acid Glucose (non-fasting) Calcium Ionised Calcium	Phosphate Total Protein Globulin Bilirubin	Aspartate Aminotransferase (AST) Lactate dehydrogenase (LD)		
Routine Urinalysis (if positive urine dipstick)	Bilirubin, Specific gravity, pH, Nitrate, Protein, Leucocyte esterase, Blood, Ketones, Glucose, Urobilinogen.	Microscopic examination (if blood or protein is abnormal)			
Pregnancy testing	Highly sensitive serum				
FSH	FSH for confirmation of post memopausal status				
Other Tests	Serology: (HIV antibody, hepatitis B surface antigen [HBsAg], and hepatitis C virus antibody)				

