## 3. SCHEDULE 1 OF OBSERVATIONS AND PROCEDURES PART A

Procedure	Day -30 to -2	Day 1/Day 4/Day 7 (hours)												Day 3/ 6	Day 14/ ETV
	Screening	Pre- Dose	Dose	5 min	0.25	0.5	1	1.5	2	2.5	3	4	6 Discharge	Day prior dosing 	+/- 2 day
Informed consent	x														
Medical history	x	x													
Inclusion/exclusion criteria	x														
Demography	x														
Physical examination, height, weight	x														
Symptom-directed physical exam		x											x		x
Pregnancy test (WOCBP) 	x	x													x
Urine drug screen, Urinalysis and Alcohol breath test 	x	x													
SARS-CoV-2 Test 															
HIV, Hepatitis B & C screening	x														
Clinical laboratory tests	x												x	x	
12-lead ECG	x	x							x				x		x
Vital signs	x	x			x	x	x	x	x	x	x	x	x		x
Spot pulse oximetry	x	x			x	x	x	x	x	x	x	x	x		x
Randomization		x													
Dose administration 			x												
AE review				x	x	x	x	x	x	x	x	x	x		x
Concomitant medication review	x	x	x	x	x	x	x	x	x	x	x	x	x		x
PK 		x		x	x	x	x	x	x			x	x		
PD 		x		x	x	x	x	x	x			x	x		
Discharge													x		

\*# Participants who withdraw early from the study will be encouraged to return to the clinic for an ETV assessment.

\* Participants may require an unscheduled visit to address safety issues and/or for any additional PK and/or PD sample collection as required.

1 All WOCBP will have a serum pregnancy test at Screening and at the ETV visit, if applicable. Urine pregnancy tests will be performed for WOCBP at all other specified subsequent visits. If a urine pregnancy test is positive, it must be confirmed by a serum pregnancy test.

2. Urine Drug Screen and Alcohol Breath Test will be performed in clinic. A urine dipstick will be completed at all visit. In the event of positive Leukocytes and/or nitrates that urine sample will be sent to the local labortaotry for a microscopic examination.

3. SARS-CoV-2 Test will be taken if clinically indicated and in line with local processes.  
 4. All participants will fast 8 hours prior and 4 hours after the study drug administration  
 5. Samples must be taken with enough time that results are available prior to planned IP dosing on the following morning.  
 6. Pre-dose, 5 ± 1 min, 15 ± 2 min, 30 ± 2 min, 60 ± 5 min, 2 h ± 10 min, 4h ± 20 min, 6h ± 30 min post-dose.

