#### 4. SCHEDULE 1 OF OBSERVATIONS AND PROCEDURES PART B

Procedure	Day -30 to -2	Day 1/Day 2 (hours)															Day 9/ ETV		
	Screening	Pre Dose	Dose	5min	10 min	15 min	20 min	30 min	45 min	1	1.5	2	2.5	3	3.5	4	5	6	+/ - 1 day
Informed consent	x																		
Medical history	x																		
Inclusion/exclusion criteria	x	x																	
Demography	x																		
Physical examination, height, weight	x																		
Symptom-directed physical exam		x															x	x	
MRI or CT if >6mths 	x																		
Sciatic Pain History	x																		
3 Day NRS Pain Scores 		x																	
Pregnancy test (WOCBP) 	x	x																x	
Urine drug screen, Urinalysis and Alcohol breath test 	x	x																	
SARS-CoV-2 Test 																			
HIV, Hepatitis B & C screening	x																		
Clinical laboratory tests	x	x															x	x	
12-lead ECG	x	x										x			x		x	x	
Vital signs	x	x								x	x	x	x	x	x	x	x	x	
Spot pulse oximetry	x	x								x	x	x	x	x	x	x	x	x	
Pain scores (VAS)		x			x			x	x	x	x	x	x	x	x	x	x	x	

Provocation Assessment with VAS		x				x		x	x	x	x	x	x	x	x	x	x	x	x	x	
Patient General Impression of Change 																			x		
QST (von Frey) 		x										x				x					
Randomization		x																			
Dose administration 			x																		
AE review				x		x		x	x	x	x	x	x	x	x	x	x	x	x	x	
PK Sampling 		X		x	x		x	x	x	x									x		
PD Sampling 		x		x	x		x	x	x	x								x			
Concomitant medication review												x							x		
Bang Binding Index assessment 																		x			
Discharge 																		x			

\*# Participants who withdraw early from the study will be encouraged to return to the clinic for an ETV assessment.

\* Participants may require an unscheduled visit to address safety issues and/or for any additional PK and/or PD sample collection as required.

1 All WOCBP will have a serum pregnancy test at Screening and at the ETV visit, if applicable. Urine pregnancy tests will be performed for WOCBP at all other specified subsequent visits. If a urine pregnancy test is positive, it must be confirmed by a serum pregnancy test.

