2. Urine Drug Screen and Alcohol Breath Test will be performed in clinic. A urine dipstick will be completed at all visit. In the event of positive Leukocytes and/or nitrates that urine sample will be sent to the local labortaotry for a microscopic examination.

3. SARS-CoV-2 Test will be taken if clinically indicated and in line with local processes.

4. All participants will fast 8 hours prior and 4 hours after the study drug administration

5. Staff to contact the participant for 3 consecutive days during the week prior to dosing for documentation of daily pain scores

6. Not required if participant has current imaging available within the last 6 months

7. Mechanical Quantitative Sensory Test (QST) assessment using Von Frey Aesthesiometer will be completed by trained staff members

8. Pre-dose, 5 (mid infusion), 10 (end of infusion)  $\pm$  1 min, 20  $\pm$  1 min, 30  $\pm$  2 min, 45 min  $\pm$  5 min, 60 min  $\pm$  5 min, 6h  $\pm$  30 min from the start of the infusion of the dose.

9. Completed 6 hours post dose on Day 2 only

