### 9.6.10. Urinalysis

A urinalysis test (dipstick) will be performed for each participant. Urinary analysis will be performed at Screening and other times according to the timepoints listed in Schedule 1 and 2 .If abnormality is noted for nitrite or leukocyte esterase (and at the discretion of the

---

Investigator) a microscopic examination of RBC, WBC, bacteria and casts will be performed by the local laboratory.

Macroscopic urinalysis parameters to be tested are:

- pH (PH)
- Specific Gravity (SPGRAV)
- Creatinine (CREATININE)
- Protein (PROT)
- Glucose (GLUC)
- Ketones (KETONES)
- Total Bilirubin (BILI)
- Occult Blood (OCCBLD)
- Nitrite (NITRITE)
- Urobilinogen (UROBIL)
- Leukocytes (WBC)

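### Urinalysis timing and microscopy triggers differ between passages, and the Part B by-treatment visit tables hold no post-dose urinalysis for either treatment

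*Protocol*

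**What the plan says.** **Timing.** Four places deal with when urine is tested.

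- Protocol 9.6.9: "Urinalysis, Urine Drug Screen and Pregnancy testing will occur at Screening, prior to each dosing occasion and Follow up visit or ETV, if applicable".
- The row "Urine drug screen, Urinalysis and Alcohol breath test" in the schedules (Protocol Sections 3 and 4) is marked at Screening and Pre-dose. It is blank at Day 3/6 and Day 14/ETV in Part A and at Day 9/ETV in Part B.
- Footnote 2, attached to that row in both schedules: "A urine dipstick will be completed at all visit".
- Protocol 9.6.10 refers back to the schedules: "Urinary analysis will be performed at Screening and other times according to the timepoints listed in Schedule 1 and 2".

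**Microscopy.** Footnote 2 says: "In the event of positive Leukocytes and/or nitrates that urine sample will be sent to the local labortaotry for a microscopic examination". Protocol 9.6.10 begins "If abnormality is noted for nitrite or leukocyte esterase" and adds the investigator's discretion. The 9.6.9 table has instead "Microscopic examination (if blood or protein is abnormal"), and SAP 12.3.1 repeats that entry.

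**Tabulation.** Protocol 21.3.3 counts urinalysis as safety laboratory data, summarised by visit and treatment, and SAP 12.3.2 adds change from baseline. SAP 3.2.1 gives each Part B period its own baseline. SAP 3.2.6 combines the Day 1 and Day 2 pre-dose records by the treatment of that period and reports Day 9/ETV for all participants together, not by treatment.

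**The concern.** Laboratory abnormalities are a Part A primary endpoint, and Protocol Section 16 names the dipstick among the ways adverse events are found. Staff who build visit worksheets from the grid will collect different urine data from staff who work from 9.6.9 or the footnote. The difference falls on the sample after the last dose, which in Part A is the highest dose.

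The trigger conflict affects interpretation. A dipstick positive only for blood or protein leads to microscopy under the 9.6.9 table and SAP 12.3.1, but not under footnote 2 or 9.6.10. For leukocytes or nitrite alone it is the other way round. When a microscopy result is absent, the analyst cannot tell whether it was not required or not done.

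The Part B table has a further problem that does not depend on the timing conflict. A by-treatment urinalysis summary with no post-dose value can be read as a clean result when it is no result.

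**Working it through.** There is no figure in the plan to reproduce. The check is a count of infusions followed by at least one scheduled urinalysis, then a trace of each Part B sample through the SAP rules.

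**Inputs.** Part A: 8 participants dosed on Days 1, 4 and 7 at 0.8, 1.2 and 1.8 mg/kg, with 6 active and 2 placebo on each day (Protocol synopsis and 7.3). Part B: up to 20 participants, 10 per sequence (SAP 2.2), 1.8 mg/kg or placebo on Day 1 and the other on Day 2. Follow-up is at Day 14 and Day 9.

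**Coverage.** On the marks alone, the only urine after a dose is the next dosing day's pre-dose sample.

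| Infusions | Marks alone | With follow-up sample (9.6.9, footnote 2) |
|---|---|---|
| Part A, 0.8 mg/kg | 6 of 6 | 6 of 6 |
| Part A, 1.2 mg/kg | 6 of 6 | 6 of 6 |
| Part A, 1.8 mg/kg (Day 7) | 0 of 6 | 6 of 6 |
| Part A, placebo | 4 of 6 | 6 of 6 |
| Part A, all (8 × 3 = 24) | 8 × 2 = 16 | 24 |
| Part B, Period 1 | 20 of 20 | 20 of 20 |
| Part B, Period 2 | 0 of 20 | 20 of 20 |
| Part B, LAT8881 only | 10 of 20 | 20 of 20 |

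SAP 2.5 expects 17 completers. If the sequences are balanced, 8 or 9 of 17 LAT8881 infusions fall in Period 2 and have no later sample on the marks. The samples are also not close to dosing: Day 1 to Day 4 is 3 days (about 72 h), while Day 7 to Day 14 and Day 2 to Day 9 are each 7 days.

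**Illustration of detection.** Counting both parts, LAT8881 at 1.8 mg/kg has 10 covered infusions on the marks and 6 + 20 = 26 with the follow-up sample. The chance of at least one abnormal result is 1 − (1 − p)^n. The documents give no rate, so p is assumed.

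| Assumed p | n = 10 | n = 26 |
|---|---|---|
| 5% | 40% | 74% |
| 10% | 65% | 94% |
| 20% | 89% | 99.7% |

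This treats an abnormality as still present when sampled, whether that is one day or seven days after dosing, so it flatters both columns.

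**Part B samples through the SAP.**

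- Day 1 pre-dose is the Period 1 baseline, filed under the Period 1 treatment.
- Day 2 pre-dose is the first urine after the Period 1 infusion. SAP 3.2.6 files it under the Period 2 treatment, and SAP 3.2.1 makes it that period's baseline. Its change from the Period 2 baseline is the value minus itself, which is 0.
- Day 9, if taken, appears in the total only.

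The by-treatment rows therefore hold two baselines and no post-dose value. The worst-case category in SAP 12.3.2 uses all post-baseline assessments but does not say to which treatment a Day 9 value belongs. The maximum-shift tables cover haematology and chemistry only. SAP 3.2.5 sets no comparable timepoint rule for Part A, so this step is confined to Part B.

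**The case against.** A reader might infer that the top dose and the whole second period cannot show a urine abnormality. The documents do not support that. Protocol 9.6.9 and the footnote on the same row both call for a later sample. The row bundles three tests, so its marks can be read as their shared minimum, with the footnote extending the dipstick. In addition, 1.8 mg/kg is also the Part B dose, and participants given LAT8881 on Day 1 have a Day 2 pre-dose urinalysis even on the marks.

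A reader might also infer that no site can comply with every passage. That is not so either. No text says "only", and a site doing a dipstick at every visit, with microscopy on any listed abnormality, would meet all of them. The triggers may even belong to successive steps, because the 9.6.9 table entry applies to laboratory urinalysis after a positive dipstick. But nothing in the documents says so.

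The clinical laboratory tests row has late post-dose marks in both parts, and urinalysis is classed as laboratory data. If that row includes urine, the gap closes. The documents do not say that it does. Urinalysis has its own row, and the 9.6.9 table makes laboratory urinalysis conditional on a positive dipstick.

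Labelling a pre-dose value with the coming treatment is normal with per-period baselines, so the Day 2 sample cannot simply be moved to Period 1. That is right, and it shapes the fix. Finally, a urine finding recorded as an adverse event would still be assigned by start date under SAP 3.2.6, so such a finding keeps its treatment label in the event tables.

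**Conclusion.** The point holds as a conflict between passages with a limited consequence. The timing texts differ, and a site following the marks alone takes no urine after the Part A Day 7 dose (0 of 6 active) or the Part B second infusion (0 of 20 planned). The microscopy triggers differ between footnote 2 and 9.6.10 on one side and the 9.6.9 table and SAP 12.3.1 on the other. In Part B, the by-treatment visit summary has no post-dose urinalysis for either treatment, and collecting Day 9 urine does not change that under the present SAP.

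This rests on three assumptions: the schedule columns are read correctly from the extracted tables, the clinical laboratory tests row does not include urine, and Part B has the planned 10 per sequence. Some support for the column reading is that the pregnancy-test rows, covered by the same 9.6.9 sentence, do keep a follow-up mark in both schedules.

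It should be put right, but it does not threaten the trial's main conclusions.

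**What to change.** - Reconcile the schedule rows, footnote 2 and Protocol 9.6.9 on whether urinalysis is done at follow-up/ETV and at the other visits. Which rule applies is for the sponsor and the investigator.
- Reconcile the microscopy trigger so that one statement appears in both footnotes, 9.6.9, 9.6.10 and SAP 12.3.1. This review does not choose it.
- In SAP 12.3.2, present the Part B Day 2 pre-dose urinalysis as the post-dose value of the Period 1 treatment, while keeping it as the Period 2 baseline.
- Show any Day 9 urinalysis by sequence, labelled with the last treatment received.
- If no urine is taken after the last dose, state that urinalysis was not assessed after the Part A Day 7 dose or in Part B Period 2.

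The cost is wording in the schedules, two protocol sections and the SAP, plus at most one dipstick at an existing visit. That sample is open only to participants not yet followed up: SAP 2.5 records a recommendation to close on 12 May 2023, with the last visit expected on 19 May 2023. The Day 2 table rule needs no new data. Its drawback is that one value serves in two roles, which a table footnote should state.

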### 9.6.10. Urinalysis

A urinalysis test (dipstick) will be performed for each participant. Urinary analysis will be performed at Screening and other times according to the timepoints listed in Schedule 1 and 2 .If abnormality is noted for nitrite or leukocyte esterase (and at the discretion of the

---

Investigator) a microscopic examination of RBC, WBC, bacteria and casts will be performed by the local laboratory.

Macroscopic urinalysis parameters to be tested are:

- pH (PH)
- Specific Gravity (SPGRAV)
- Creatinine (CREATININE)
- Protein (PROT)
- Glucose (GLUC)
- Ketones (KETONES)
- Total Bilirubin (BILI)
- Occult Blood (OCCBLD)
- Nitrite (NITRITE)
- Urobilinogen (UROBIL)
- Leukocytes (WBC)

#### **9.6.11. Urine Drug Screen**

A Urine drug screen will be performed at screening and other times according to the study schedule.

Urine drug screen to include at minimum:

- Amphetamines
- Barbiturates
- Cocaine
- Opiates
- Cannabinoids
- Benzodiazepines

A positive drug screen will result in exclusion from the study unless there is documentation of a stable dose of prescribed medication therapy for participants enrolled in Part B.

